8.6 Pharmacodynamics

Blood sampling for PD parameters is scheduled for the time points as given in Section 8.5.1. The actual date and time of blood sampling will be documented in the eCRF. All PD parameters will be measured using validated methods.

Quality control and calibration samples will be analyzed concurrently with study samples. For selected PD parameters, the results of quality control samples will be reported together with analyte concentrations in the Clinical Study Report of this study.

Analyte results are calculated according to the method description. Detailed method descriptions of all PD methods will be filed with the study report.

8.6.1 Secondary pharmacodynamic parameters:

The following parameters will be used to assess the PD effects after administration of the investigational drug, but may be performed optionally and/or only in a subset of participants:

- Factor XI activity will be assessed with an aPTT-based coagulation test using FXI deficient plasma. Furthermore, the assay will be conducted after in vitro neutralization of heparin in order to separate potential heparin effects from the PD effect of BAY 297621
- FXI antigen concentration will be measured via enzyme-linked immunosorbent assay using polyclonal antibodies

8.6.2 Other Pharmacodynamic parameters:

The following parameters will be used to assess the PD effects after administration of the investigational drug, but may be performed optionally and/or only in a subset of participants:

- aPTT will be measured using a standard clotting assay. Furthermore, the aPTT assay will be conducted after in vitro -neutralization of heparin in order to separate potential heparin effects from the PD effect of BAY 297621
- AXIA will be analyzed using a kaolin-trigger and a fluorogenic substrate readout
- PT (seconds and INR) will be determined using standard methods
- D-Dimer will be measured using an immunoturbidometric method
- TAT and F1.2, will be analyzed using immunoassays
- SQCS will be analyzed as described below

07 JUL 2021 Page: 60 of 90

Semi-quantitative Clotting Score: Extent and frequency of clotting on the dialysis filters & circuit

The rate/frequency of clotting on the dialysis filters and circuit will be measured as an exploratory PD analysis. The effect of BAY 2976317 on the clotting in the dialysis circuit will be assessed by the SQCS. The clotting assessment is a quantitative scale by descriptive category that is performed by trained personnel.

At the end of the hemodialysis procedure, at specified time points, the filter and line (including drip chamber/air trap) will be examined by the hemodialysis nurse (or respective appropriate personnel) after rinsing the circuit. Clotting scores will be assigned as follows:

- "0" clean filter and no visible clots in the drip chamber/air trap
- "1" traces of coagulation in the filter and/or in the drip chamber/air trap
- "2" intermediate state between "1" and "3"
- "3" fully clotted extracorporeal system resulting in an interruption of the hemodialysis session

Adequate anticoagulation is defined by a SQCS of less or equal "1".

Overall score is the highest of the individual component scores:

Inspection Site	Category 0	Category 1	Category 2	Category 3
Drip chamber (also referred to as air trap)	No visible clots in the drip chamber	Trace (e.g fibrinous ring with no clot formation on venous chamber)	Intermediate (e.g clot formation on venous chamber, more than "1" but not fully clotted)	Fully clotted system (treatment cannot continue without new setup)
Dialyzer	Clean dialyzer	Trace (e.g blood stripes affecting less than approximately 5% of the fibers seen at the surface of the dialyzer)	Intermediate (e.g blood stripes affecting approximately 5% or more of the fibers seen at the surface of the dialyzer, but not fully clotted)	Fully clotted filter

Only one (highest) score will be documented in the eCRF.

The clotting score will be recorded as specified in the SoA. The dialyzer and drip chamber/air trap will be assessed for clotting score at the end of the dialysis session on the visit day (or from a dialysis session within the visit window if the visit is not conducted on a dialysis day).

For information on PD sampling see Section 8.5.

The study sponsors reserve the right not to conduct all or part of the above-mentioned analysis.

8.7 Genetics

Genetic as well as non-genetic analyses will be part of the biomarker investigations in this study. Genetic investigations may be of any kind, except for whole genome sequencing.

8.8 Biomarkers

Exploratory biomarker analyses (scheduled for the time points as given in Section 1.3), that might be performed optionally and/or only in a subset of participants are:

07 JUL 2021 Page: 61 of 90

- FVIII, FIX and FXII activity using clotting assay (V5 only)
- vWF antigen and vWF risocetin cofactor activity (V5 only)
- TAFI and C1 inhibitor activity, measured using chromogenic substrate assays

In addition to the biomarkers described above, further biomarkers related to the mode of action or the safety of BAY 2976217 and similar drugs may be examined. The same applies to further biomarkers deemed relevant to cardiovascular and renal diseases and associated health problems. These investigations may include e.g. diagnostic, safety, PD, monitoring, or potentially predictive biomarkers.

Furthermore, some PD markers listed under Section 8.6 may also be analyzed using alternative reagent/analyzer manufacturers in order to assess potential systematic influences of the analysis technology. The additional analyses may include genetic as well as nongenetic biomarkers. Results will be reported under separate cover, if the evaluations are performed.

Details on the collection, processing, storage, and shipment of biomarker samples will be provided in separate documents (e.g., sample handling sheets or lab manual). Samples may be stored for a maximum of 15 years (or according to local regulations) following the end of the study at a facility selected by the sponsor to enable further analyses.

8.9 Immunogenicity Assessments

Antibodies to BAY 2976217 will be evaluated in samples collected from all participants according to the SoA (Section 1.3). Additionally, samples should also be collected at the final visit from participants who discontinued study intervention or were withdrawn from the study. These samples will be tested by the sponsor or sponsor's designee.

Samples will be screened for antibodies binding to BAY 2976217 and the titer of confirmed positive samples will be reported. Other analyses may be performed to verify the stability of antibodies to BAY 2976217 and/or further characterize the immunogenicity of BAY 2976217.

The detection and characterization of antibodies to BAY 2976217 will be performed using a validated assay method by or under the supervision of the sponsor. Samples collected for detection of antibodies to study intervention may also be evaluated for BAY 2976217 concentration to enable interpretation of the antibody data. Antibodies may be further characterized and/or evaluated for their ability to neutralize the activity of the study intervention. Samples may be stored for a maximum of 15 years (or according to local regulations) following the last participant's last visit for the study at a facility selected by the sponsor to enable further analysis of immune responses to BAY 2976217.

For information on immunogenicity sampling see Section 8.5.1.

8.10 Health Economics

Not applicable

07 JUL 2021 Page: 62 of 90

9. Statistical Considerations

9.1 Statistical Hypotheses

There is no plan for statistical hypothesis testing for this study.

9.2 Sample Size Determination

No formal statistical samples size estimates were performed.

The sample size was selected based on prior experience in ESRD with the unconjugated ASO. This study is planned to ensure the safety, tolerability, and PK/PD relationships are assessed adequately while minimizing unnecessary participant exposure. There is no plan for statistical hypothesis testing for this study. In this study, the number of subjects is considered based on the ISIS 416858-CS5 study design.

Approximately 288 participants (96 [72 active+24 placebo] per cohort) will be randomly assigned to study intervention so that an estimated 240 participants will complete the main treatment period. A participant will be evaluated once he/she was randomized and received at least one dose of study intervention, the number of evaluable and randomized participant is assumed to be similar. Considering an approximately 15% dropout rate, an estimated total of 60 participants per intervention group and the placebo group will complete the main treatment period. All participants will be randomized to 1 of 3 dose cohorts in a 1:1:1 ratio (Cohort A, Cohort B, and Cohort C). Within each dose cohort, subjects will be randomized in a 3:1 ratio to receive treatment with either BAY 2976217 or placebo.

Note: "Enrolled" means a participant's, or their legally acceptable representative's, agreement to participate in a clinical study following completion of the informed consent process.

Table 9–1 summarizes 95% expected range for the true population proportion of participants with the composite of MB and CRNMB bleeding. For example, with 60 participants, if 5% had the composite of MB and CRNMB bleeding during the main treatment period and the desired confidence level is 95%, the corresponding confidence interval would be \pm 5.51, i.e. the range of 0.0 % to 10.51%. If multiple samples were drawn from the same population and a 95% CI calculated for each sample, we would expect the true population proportion to be found within 95% of these CIs.

Table 9–1: Confidence Interval for proportion of participants with composite of MB and CRNMB Bleeding

Sample Size	Observed Proportion *	Desired Confidence level	Corresponding two-sided confidence interval	Range for the true population proportion
60	2%	95%	±3.54	0.0% to 5.54%
	3%	95%	±4.32	0.0% to 7.32%
	4%	95%	±4.96	0.0% to 8.96%
	5%	95%	±5.51	0.0 % to 10.51%
	6%	95%	±6.01	0.0% to 12.01%
	7%	95%	±6.46	0.54% to 13.46%
	8%	95%	±6.86	1.14% to 14.86%

CRNMB = clinically relevant non-major bleeding, MB = major bleeding

^{*} The range of observed proportion is considered based on the Interim report of ISIS 416858-CS5 study where composite of MB and CRNMB bleeding proportion for Placebo was 5.7% and for total ISIS treated= 4.5% (ISIS treated with 200mg, 250mg and 300 mg doses were 3.8%, 5.6% and 4.0% respectively)

07 JUL 2021 Page: 63 of 90

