9.4.1 General considerations

9.4.1.1 Planned Methods of Analysis

Descriptive statistics will be provided by treatment group for all demographic variables, safety endpoints, and exploratory endpoints. The placebo groups from each cohort will be combined, so that there are four treatment groups to be included for analysis—40 mg, 80 mg, 120 mg, and placebo, all equal in size.

- The safety analysis set will be used for all safety endpoints, including the primary endpoint.
- The full analysis set will be used for the exploratory endpoints or otherwise specified.
- The PK analysis set will be used for the pharmacokinetic endpoints, and
- The PD analysis set will be used for the pharmacodynamics endpoints.

For categorical variables, frequencies and proportions will be provided by treatment group. For continuous variables, means, medians, standard deviations, standard error of mean, interquartile range (25th percentile, 75th percentile), and range (minimum, maximum) will be provided by treatment group. For continuous variables collected at multiple time points, the descriptive statistics will be provided at each time point.

All analyses and tabulations will be performed using SAS@ Version 9.2 or higher or if applicable, other software.

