9.4.2 Primary endpoint(s)

The primary endpoint is the incidence of the composite of major bleeding and clinically-relevant non-major bleeding, as assessed by blinded CIAC.

Estimand for the primary safety endpoint:

The five attributes of the estimand are as follows:

- **Population:** ESRD patients as described by the inclusion/exclusion criteria given in Section 5.
- **Variable:** The incidence of composite of MB and CRNMB during the main treatment period, as assessed by CIAC.
- **Treatment:** Three dose groups of BAY 2976217 or placebo

• Intercurrent events:

- Unblinding to study intervention: the study allows unblinding of the intervention code: regardless of whether such an event occurs (treatmentpolicy strategy)
- Early definitive discontinuation of study treatment or death or kidney transplant: until the occurrence of the intercurrent event (while on-treatment strategy)
- Dose reduction: regardless of whether such an event occurs (treatment-policy strategy).
- **Population-level summary:** Proportion of subjects with a bleeding event by study intervention groups.

07 JUL 2021 Page: 66 of 90

The primary objective is to assess the safety of the three different doses of BAY 2976217 given once a month which is expected to be maintained during a chronic treatment. The primary safety analysis is based on a descriptive proportion of subjects with bleeding events based on the Safety analysis population. (see Section 9.3).

- All suspected events of bleeding will be reported as an AE or SAE as per adverse event reporting procedure in Section 8.3. Additionally, an adjudication package will be sent to the CIAC. The CIAC will classify bleeding as defined in Section 8.2.1.
- Proportion of subjects with bleeding events including the following categories will be tabulated by treatment as assessed by the CIAC:
 - Composite of MB and CRNMB
 - o MB
 - o CRNMB
 - o Minor bleeding
- For the primary safety analysis, primary safety outcomes will be considered during the main treatment period and while on-treatment. Incidences of MB, CRNMB, minor bleeding will be analyzed similarly.

The frequency and percentage of participants with bleeding will be reported where the denominator will be total number of participants in each treatment group in the safety analysis set. The corresponding exact binomial 95% confidence interval will be provided.

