6.4.1 Analysis of the Primary Safety Variable

The primary analysis is based on a descriptive proportion of subjects with primary endpoints (independently adjudicated) based on SAF analysis set and PA data scope. For each treatment and bleeding category, participants reporting more than one bleeding event will be counted only once using the highest severity. The frequency and percentage of participants with bleeding will be reported where the denominator will be total number of participants in each treatment group.

Estimand for the Primary Safety Endpoint:

The five attributes of the estimand are as follows:

- **Population:** The population consists of ESRD patients as described by the inclusion/exclusion criteria given in study protocol.
- Variable: The incidence of the composite of MB, CRNMB, events during the main treatment period, as assessed by the CIAC
- Treatment: Three dose groups of Fesomersen or placebo on top of standard of care
- Intercurrent events:
 - Unblinding to study intervention: the study allows unblinding of treatment assignment if the investigator deems necessary when related a bleeding or major surgery occur regardless of whether such an event occurs (treatment-policy strategy)
 - Early definitive discontinuation of study intervention or death or kidney transplant: until the occurrence of the intercurrent event (while on treatment strategy)
 - Dose reduction: regardless of whether such an event occurs (treatment-policy strategy).
- **Population-level summary:** Incidence proportion of subjects with an event by study intervention group and differences between Fesomersen treatment groups and placebo group. For the incidence proportions the exact binomial two-sided 95% confidence interval using Blaker's method will be provided. For the difference in incidence proportions the two-sided 95% confidence interval will be presented using the unstratified exact method with the standardized test statistic and inverting a two-sided test (Agresti and Min, 2000).

6.4.1.1 Additional Primary Safety Endpoint(s) Analysis:

Estimand for Time to Event Safety Endpoint:

The attributes constituting the estimand for this endpoint are the following:

- **Population:** The population consists of ESRD patients as described by the inclusion/exclusion criteria given in study protocol.
- Variable:
 - Time from first dose of intervention to MB and CRNMB events (in alignment with ISTH guidelines) up until 28 days after last study intervention

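### The only stated precision for the primary bleeding endpoint (Protocol Table 9-1, SAP Table 4-1) uses normal-approximation limits for 60 completers, whereas the planned interval is exact on about 72 treated per group; stated upper limits are about 1.5 to 2.5 points too low

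*Protocol*

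**What the plan says.** Protocol 9.2 gives no formal sample size calculation and Protocol 9.1 plans no hypothesis test. In their place, Table 9-1 shows a half-width and a range for observed proportions of 2% to 8% with n=60. The worked example takes 5% of 60, a half-width of 5.51, "i.e. the range of 0.0 % to 10.51" percent. SAP 4.7 repeats the text and the numbers as Table 4-1. Neither document names the method behind the table.

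The 60 is a completer count: "an estimated total of 60 participants per intervention group and the placebo group will complete the main treatment period". The same paragraph says a participant is evaluated once randomized and dosed, and that "the number of evaluable and randomized participant is assumed to be similar". After the example it adds that, over repeated samples, "we would expect the true population proportion to be found within 95% of these CIs".

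The analysis sections specify something else:

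- Protocol 9.4.1.1: "The safety analysis set will be used for all safety endpoints, including the primary endpoint".
- Protocol 9.4.2: "the denominator will be total number of participants in each treatment group in the safety analysis set", followed by "The corresponding exact binomial 95% confidence interval will be provided".
- SAP 6.4.1, for the incidence proportions: "exact binomial two-sided 95% confidence interval using Blaker's method will be provided".

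**The concern.** The table should describe the interval that will be reported, and it does not. It uses a Wald interval where an exact one is planned, and completers where everyone dosed is planned. At event rates of a few percent and group sizes of 60 to 72, the Wald upper limit is known to be too low, and the upper limit is what matters for a bleeding endpoint. Five of the seven rows also show a lower limit of 0.0%, which an exact method cannot give once one event has been seen.

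With no test and no power statement, this is the only place where either document says how precisely the primary endpoint will be estimated. Someone using it to judge which bleeding rates the trial can rule out before Phase 3 dose selection would be misled in the favourable direction.

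**Working it through.** **Inputs.** Table 9-1: n=60, observed 2% to 8%, 95% two-sided. Protocol 9.2: 72 active and 24 placebo per cohort, so 72 per dose group and 3 × 24 = 72 pooled placebo. About 15% dropout: 72 × 0.85 = 61.2, which the plan takes as 60. Protocol 9.3: the safety set is everyone randomized with at least one dose. With evaluable and randomized numbers assumed similar, the planned denominator is about 72.

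**Step 1: reproduce the table.** Half-width = 1.96 × √(p(1−p)/60), lower limit cut at 0. For p = 0.05: 1.96 × √(0.05 × 0.95/60) = 5.51 points, upper limit 10.51%. The seven half-widths come out as 3.54, 4.32, 4.96, 5.51, 6.01, 6.46 and 6.86, and all seven upper limits match. With n=72 the same formula gives 5.03 at 5%, which does not match.

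**Step 2: the planned interval.** Blaker's interval holds every p for which the following sum exceeds 0.05: the smaller tail probability at the observed count, plus the largest opposite-tail probability not exceeding it. For x events out of 72:

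| Events | Observed | Blaker 95% |
|---|---|---|
| 0 | 0% | 0–4.95% |
| 1 | 1.39% | 0.07–7.14% |
| 2 | 2.78% | 0.50–9.25% |
| 3 | 4.17% | 1.15–11.35% |
| 4 | 5.56% | 1.92–13.43% |
| 5 | 6.94% | 2.78–14.92% |
| 6 | 8.33% | 3.69–16.96% |

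**Step 3: compare upper limits.** None of the tabulated percentages is a whole count out of 72, and only 5% (3/60) is one out of 60. Blaker limits are therefore interpolated between whole counts, for comparison only.

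| Observed | Stated upper | Blaker, n=72 | Gap, n=72 | Gap, n=68 | Gap, n=60 |
|---|---|---|---|---|---|
| 2% | 5.54 | 8.07 | 2.5 | 2.8 | 3.5 |
| 3% | 7.32 | 9.59 | 2.3 | 2.6 | 3.3 |
| 4% | 8.96 | 11.1 | 2.1 | 2.4 | 3.2 |
| 5% | 10.51 | 12.6 | 2.1 | 2.4 | 3.1 |
| 6% | 12.01 | 13.90 | 1.9 | 2.3 | 3.1 |
| 7% | 13.46 | 15.00 | 1.5 | 1.9 | 3.0 |
| 8% | 14.86 | 16.47 | 1.6 | 1.9 | 2.7 |

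**Step 4: attainable results, no interpolation.** For 3/60, Blaker gives 1.38–13.63% against the stated 0.0–10.51%. For 3/72, the Blaker upper limit is 11.35%; the table's formula (Wald, n=60) at that proportion gives 9.22%. For 4/72 the two are 13.43% and 11.35%.

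**Step 5: separate the two mismatches.** Moving from 60 to 72 within the Wald formula lowers the upper limits to between 5.23% (2% row) and 14.27% (8% row), a fall of 0.3 to 0.6 points. The denominator therefore works in the conservative direction. The shortfall comes from the interval method, and the completer denominator hides part of it.

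**Step 6: the coverage sentence.** Exact coverage of the Wald interval at n=60 is the sum of binomial probabilities over the counts whose interval contains the true rate:

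| True rate | 2% | 3% | 4% | 5% | 6% | 7% | 8% |
|---|---|---|---|---|---|---|---|
| Coverage | 70.1% | 83.7% | 91.1% | 80.6% | 87.9% | 92.1% | 86.1% |

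Over a fine grid from 2% to 8% the maximum is 94.9%. The low values at 2% to 4% come almost entirely from the zero-event sample, whose Wald interval has zero width. Giving that one sample an exact interval lifts coverage above 99% at 2%, 3% and 4%, but at 5%, 6%, 7% and 8% it is still 85.2%, 87.9%, 92.1% and 86.1%. Blaker coverage over the same range is at least 95% at both n=60 and n=72.

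**The case against.** The case for leaving the table alone has five parts.

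- **The arithmetic is right for its formula, and nothing depends on it.** No test is planned, N follows the earlier study's design, no bleeding rate is named that must be excluded, and the exact interval on the safety set is already prespecified. All of this stands and limits the point to stated precision.
- **Using 60 instead of 72 is conservative.** Also true, as Step 5 shows. It does not rescue the table: at n=60 the gap to the planned method is larger, 2.7 to 3.5 points.
- **The size depends on convention.** Interpolation is needed, and the Protocol says only exact binomial, so Clopper-Pearson would also qualify. That method gives higher upper limits (11.70% for 3/72, 13.92% for 3/60) and gaps of about 2.0 to 2.9 points. The direction does not change.
- **The coverage sentence merely defines a confidence interval, and no Wald interval will be reported for this proportion.** As a definition of nominal confidence it is fine. But it refers to the intervals just tabulated, and for those it is untrue.
- **It is late.** SAP 6.5 indicates that the primary analysis was complete before SAP version 4.0, so a correction cannot inform design. New single-group limits would also leave the precision of the differences from placebo unstated. Both are fair; the gain is an accurate record of what the design could show.

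**Conclusion.** The concern holds. Table 9-1 and its copy in the SAP describe neither the planned interval nor the planned denominator, and every stated upper limit is below the planned one. The shortfall is 1.5 to 2.5 percentage points with Blaker at 72 per group, 1.9 to 2.8 if 68 are dosed, and 2.7 to 3.5 at the table's own 60. In plain terms, 3 events in 60 are said to exclude true rates above 10.5%, while the planned method excludes only those above 13.6%; with 72 dosed, 3 events exclude rates above 11.35% and 4 events rates above 13.43%.

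This rests on about 72 dosed per group, which is the plan's own assumption, and on Blaker as the exact method, which only the SAP names. The point is minor: it affects the stated precision, not the sample size, the analysis or any reported result.

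**What to change.** In Protocol 9.2 and SAP 4.7, replace the table and worked example with Blaker limits by whole event count at n=72, using the 0 to 6 event rows in Step 2 of the working. If a worst case is wanted, add n=60 (3/60: 1.38–13.63%). Name the method in the table title, and change the coverage sentence to say at least 95%.

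The minimum alternative is one line labelling the table a normal approximation for 60 completers that is not the planned interval, with the coverage sentence deleted.

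The cost is one table and two sentences in each document, or one label and one deletion, plus the usual document-change process. No extra participants are needed and no analysis changes. The stated upper limits become about 1.5 to 2.5 points less favourable.
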